3.2.3 Exclusion criteria related to systemic lupus erythematosus and other diseases

20. History of, or current diagnosis of, a clinically significant non-SLE-related vasculitis syndrome (see [Appendix G](#)). Subjects who have experienced vasculitis as a feature of their SLE can be recruited to the study
21. History or evidence of suicidal ideation (severity of 4 [active: method and intent, but no plan] or 5 [active: method, intent, and plan]) within the past 6 months; or any suicidal behaviour within the past 12 months based on an assessment with the Columbia-Suicide Severity Rating Scale (C-SSRS) at screening or at baseline
22. Active severe or unstable neuropsychiatric SLE including, but not limited to: aseptic meningitis, cerebral vasculitis, myelopathy, demyelination syndromes (ascending, transverse, acute inflammatory demyelinating polyradiculopathy), acute confusional state, impaired level of consciousness, psychosis, acute stroke or stroke syndrome, cranial neuropathy, status epilepticus, cerebellar ataxia, and mononeuritis multiplex:
- (a) That might cause the subject to be unable to fully understand the ICF or
 - (b) In the opinion of the Investigator, protocol-specified SOC is insufficient to control neurologic features of SLE and utilisation of a more aggressive therapeutic approach, such as adding IV cyclophosphamide and/or high-dose IV pulse corticosteroid therapy or other treatments not permitted in the protocol, is indicated or anticipated

23. Documented history of systemic sclerosis or diagnosis of SLE with overlap systemic sclerosis
24. History of, or current diagnosis of, catastrophic anti-phospholipid syndrome (APS), see [Appendix P](#)) or APS-related thromboembolic event or pregnancy loss within 1 year prior to signing the ICF. Subjects with APS adequately controlled by anticoagulants or aspirin for at least 12 weeks can be recruited to the study
25. History of any non-SLE disease that has required treatment with oral or parenteral corticosteroids for more than a total of 2 weeks within the last 24 weeks prior to signing the ICF

3.2.4 Exclusion criteria related to infection and malignancy risk factors

26. Known history of a primary immunodeficiency (eg, common variable immunodeficiency syndrome), splenectomy, or any underlying condition that predisposes the subject to infection, or a positive result for human immunodeficiency virus (HIV) infection confirmed by central laboratory at screening
27. Confirmed positive test for hepatitis B serology for:
 - (a) Hepatitis B surface antigen (HbsAg), or
 - (b) Hepatitis B core antibody (HBcAb) and hepatitis B virus (HBV) DNA detected above the lower limit of quantitation (LLOQ) by reflex testing by the central laboratory at screening

Note: Subjects who are HBcAb positive at screening will be tested monthly for HBV DNA. To remain eligible for the study, the subject's HBV DNA levels must remain below the LLOQ as per central laboratory.

A reflex test is a test that must be performed based on the results of a prior test (pre-set criteria).

28. Positive test for hepatitis C antibody
29. Any severe herpes infection at any time prior to randomisation (Week 0 visit), including but not limited to, disseminated herpes, herpes encephalitis, or ophthalmic herpes
30. Recurrent herpes zoster (defined as 2 episodes within 2 years) within 5 years prior to randomisation

31. Any herpes zoster infection that has not completely resolved within 12 weeks prior to signing the ICF
32. History of opportunistic infection (see Section 6.4.2 for definition) requiring hospitalisation or parenteral anti-infective treatment within 3 years prior to randomisation (vaginal, oral and skin candidiasis is not an exclusion reason)
33. Cytomegalovirus and/or Epstein–Barr virus infection that has not been completely resolved within the 12 weeks prior to signing the ICF
34. Either of the following:
 - (a) Clinically significant chronic infection (ie, osteomyelitis, bronchiectasis, etc.) which is not resolved within 8 weeks prior to signing the ICF (chronic nail infections are allowed)
 - (b) Any infection requiring hospitalisation or treatment with IV anti-infectives not completed at least 8 weeks prior to randomisation
35. Any infection requiring oral anti-infectives (including antivirals) within 2 weeks prior to randomisation, except chronic suppressive antiviral treatment for herpes simplex virus in the absence of active lesions within 2 weeks prior to randomisation
36. History of cancer, apart from:
 - (a) Squamous or basal cell carcinoma of the skin treated with documented success of curative therapy ≥ 12 weeks prior to randomisation (Week 0 visit)
 - (b) High-grade squamous intraepithelial lesion (CIN III, CIS) treated with apparent success with curative therapy ≥ 1 year prior to randomisation (Week 0 visit)

For procedures for withdrawal of incorrectly enrolled subjects, see Section 3.4.

3.3 Subject enrolment and randomisation

Investigator(s) should keep a record of subjects considered for, and included in the study. The pre-screening/screening log will be evaluated periodically during routine monitoring visits.

The Investigator(s) will:

1. Obtain signed informed consent from the potential subject before any study specific procedures are performed. The subject is considered enrolled when the ICF is signed and the enrolment call is done in the interactive voice/web response system (IXRS).

2. IXRS will assign the subject with a unique enrolment number. The subject ID will be pre-fixed with 'E' in IXRS reports and on the screen (sites will have to enter the 7 digit subject ID into the IXRS to retrieve subject data)
3. Determine subject eligibility. During the screening period, the study Medical Monitor/Designee will confirm eligibility criteria based on the data captured in the electronic data capture (EDC) system, and from the central laboratory. Sites will be notified to either randomise the subject or to consider the subject as screen failed, prior to the planned randomisation date.
4. On Day 1, the Investigator will confirm that all eligibility criteria are still fulfilled and will then perform the randomisation transaction in the IXRS.
5. At randomisation the IXRS will assign eligible subjects a unique randomisation code and blinded IP kit number(s) to the subject.

See additional information in Section [3.5](#).

Randomisation will be stratified using two factors:

- Results of IFN test at screening using a 4-gene type I IFN test (IFN test-high versus IFN test-low)
- 24-hour UPCR ≤ 3.0 mg/mg versus > 3.0 mg/mg (within 14 days prior to the expected date of randomisation). Without the second (stratification) sample, subjects cannot be randomised. Turn-around time for results from central laboratory is up to 7 days. On rare occasion an extension of the 30-day screening window may be allowed if the re-collection of the 24-hour UPCR or other required samples is necessary or if the results needed for randomisation are delayed.

IP (anifrolumab or placebo) should, if possible, be administered the same day the IP kit number is assigned.

3.4 Procedures for handling incorrectly enrolled or randomised subjects

Subjects who fail to meet the eligibility criteria should not, under any circumstances, be enrolled or receive IP and Sponsor-provided MMF. There can be no exceptions to this rule. Subjects who are enrolled, but subsequently found not to meet all the eligibility criteria must not be randomised or initiated on treatment, and must be withdrawn from the study.

Where a subject does not meet all the eligibility criteria but is randomised in error, or incorrectly started on treatment, the Principal Investigator should inform the Sponsor/Designee Medical Monitor immediately, and a discussion should occur between the

Sponsor/Designee Medical Monitor and the Principal Investigator regarding whether to continue or discontinue the subject from treatment. The Sponsor/Designee must ensure all decisions are appropriately documented.

3.5 Methods for assigning treatment groups

On Day 1, the Investigator will confirm that all eligibility criteria and will then perform the randomisation transaction in the IXRS. The IXRS will assign eligible subjects a unique randomisation code and blinded IP kit number(s).

Specific information concerning the use of the IXRS will be provided in the separate user manual.

Block randomisation using an IXRS will be used to randomise subjects in a 1:1:1 ratio to receive one of the two IV dosing regimens of anifrolumab (Basic Regimen/Intensified Regimen) or placebo. AstraZeneca Biostatistics group is responsible for generating the randomisation scheme for this study using the GRandom system.

3.6 Methods for ensuring blinding

This is a double-blind study in which anifrolumab and placebo are distinguishable during the final preparation step of the investigational infusion bag. Hence, the IP will be prepared by a trained unblinded team member at the site, who will not be involved in the management of study subjects.

To ensure blinding of the anifrolumab regimens, the duration of infusion is no less than 60 minutes for the first 3 doses of IP (Visits 1, 2, and 3) for all three arms.

All packaging and labelling of IP is done in such way as to ensure blinding for all Sponsor/Designee and investigational site staff, other than the unblinded team member who is assigned to prepare the IP. The kits on the shelf, and the infusion bags when prepared, look identical. Neither the subject nor any of the Investigators or Sponsor/Designees who are involved in the treatment or clinical evaluation and monitoring of the subjects will be aware of the treatment received. In the event that the treatment allocation for a subject becomes known to the Investigator or other study staff involved in the management of study subjects, the Sponsor/Designee must be notified immediately by the Investigator.

Investigators and subjects who continue in the second year extension period will continue to be blinded to their treatment. However, the Sponsor and Sponsor's delegates who are not directly involved in the management of sites will be unblinded at the time of the primary analysis at Week 52.

3.7 Methods for unblinding

The treatment code should not be broken except in medical emergencies when the appropriate management of the subject requires knowledge of the treatment randomisation. The

Investigator must document and report the action to AstraZeneca or designee, without revealing the treatment given to subject to the AstraZeneca staff or the designee. Instructions for unblinding an individual subject's IP allocation are contained in the IXRS manual. In general, unblinding should only occur if management of the medical emergency would be different based on the subject having received IP. In the majority of cases, the management of a medical emergency would be the same whether or not IP was received by the subject. If this was the case, the IP allocation should not be unblinded. Subjects who have been unblinded by the Investigator must be discontinued from IP.

One interim analysis may be conducted after approximately 50% of subjects have completed the Week 52 visit. CCI [REDACTED]

CCI [REDACTED]

[REDACTED] Details of the interim analysis including a description of who will be unblinded will be specified in the interim analysis and communication plans prior to unblinding.

After all randomised subjects have completed the 52 week double-blind period the data base will be soft-locked, and the **primary analysis** will be performed, including the assessment of the primary, secondary, and safety objectives. This analysis will also encompass available data collected after the 52 week time point and details will be provided in the SAP. At this stage the Sponsor and Sponsor's delegate who are not directly involved in the management of sites will be unblinded to randomised treatment, but the subjects and investigators will remain blinded (single-blind). The **end of study analysis** will be performed after all subjects have completed the second year extension period.

AstraZeneca or its designee retains the right to break the code for SAEs that are unexpected and are suspected to be causally related to an IP and that potentially require expedited reporting to regulatory authorities. Treatment codes will not be broken for the planned analyses of data until all decisions on the evaluability of the data from each individual subject have been made and documented.

Subjects who have been unblinded by AstraZeneca Patient Safety or designee (and who have not been unblinded to the Principal Investigator or Sponsor/Designee Medical Monitor) will not, based on the unblinding alone, be discontinued from further receipt of IP.

Individual treatment codes, indicating the treatment randomisation for each randomised subject, will be available to the Investigator(s) or pharmacists at the study site.

Live unblinded randomisation data will be periodically released to an independent PK analyst and an independent immunogenicity samples analyst from PPD, in order to allow them to perform laboratory PK and immunogenicity analysis. The unblinded randomisation data will be only released to specific named personnel for this purpose and will not be made available to any staff from AstraZeneca or Sponsor's delegate.

3.7.1 Unblinding for Data and Safety Monitoring Board

An independent DSMB will review safety data throughout the study. The DSMB will be provided with partially unblinded data (data that are summarised by treatment group using masked treatment group labels). The DSMB may choose to unblind the data for additional review as specified in the DSMB charter. The Sponsor/Sponsor's delegate study team will remain blinded to all data transfers provided to the DSMB. Details about the DSMB will be included in the DSMB charter. For further details on the DSMB, see Section 1.5.1.

3.8 Restrictions

3.8.1 Fasting lipid profile

Subjects will be required to fast for at least 8 hours prior to assessment of lipid profile at the visits described in the Treatment Period Study Plan (Table 2 and Table 4). If the subject has not fasted, he/she should fast before the next visit, and the test can be done at that visit.

3.8.2 Perioperative management of investigational product

Planned surgeries should be avoided during the study if clinically feasible.

3.8.2.1 Major surgeries

Pre-operative management of IP: If a non-urgent major surgery becomes necessary during the study, it should be scheduled at least 4 weeks after the last administration of IP, if clinically feasible. The determination of whether or not a surgery is "urgent" will be at the discretion of the investigator, preferably in consultation with the Sponsor/Designee Medical Monitor.

3.8.2.2 Non-major surgeries

The decision to withhold IP administration is at the Investigator's discretion.

Post-operative management of IP: IP administration can be resumed at the Investigator's discretion after all of the following criteria are met:

- External wound healing is complete and
- Any post-operative antibiotic course is completed and
- All acute surgical complications have resolved

3.8.3 Blood donation

Subjects must not donate blood from date of randomisation until 6 weeks after the last dose of Sponsor-provided MMF and within 12 weeks after the last IP dose.

3.9 Discontinuation of investigational product

3.9.1 Criteria for discontinuation of investigational product due to worsening LN or SLE (at any time)

Blinded IP will be discontinued in subjects who meet pre-defined criteria for worsening LN or SLE. Subjects may receive rescue treatment as clinically indicated. Subjects who had their IP discontinued will be followed according to the study schedule. These subjects will be followed until Week 52 (or for a minimum of 12 weeks after last dose of IP for subjects for whom IP was discontinued within 12 weeks prior to Week 52). If discontinuation occurs during the second year extension period, subjects will be followed until Week 104 (or for a minimum of 12 weeks after last dose of IP for subjects for whom IP was discontinued within 12 weeks prior to Week 104).

- >30% decrease in eGFR compared to baseline due to LN and eGFR <60 mL/min/1.73 m² (on two independent samples) or
- Increase in renal or extra-renal lupus activity requiring prohibited systemic immunosuppressive treatment (eg, cyclophosphamide, rituximab, belimumab)
- Receipt of >1 methylprednisolone pulse after the day of randomisation
- Receipt of any methylprednisolone pulse after Week 8
- The IP will be discontinued if MMF is discontinued and another immunosuppressant is initiated

3.9.2 Criteria for discontinuation of investigational product for worsening of LN or SLE at Week 12 and Week 24

- eGFR <75% of baseline and <60 mL/min/1.73 m² (on two independent samples) or
- Nephrotic range UPCR (confirmed by a second measurement at least two weeks after the first measurement):
 - Subjects with 24-hour UPCR ≤3 mg/mg at baseline will be withdrawn if 24-hour UPCR increases by >50% from baseline to >3.5 mg/mg

- Subjects with 24-hour UPCR >3 mg/mg at baseline will be withdrawn if 24-hour UPCR at Week 24 >3.5 mg/mg and there is $<60\%$ improvement from baseline or
- Inability to adhere to corticosteroids requirements:
 - Inability to reduce OCS to ≤ 15 mg/day prednisone-equivalent at Week 12
 - Inability to reduce OCS to <15 mg/day by Week 24

Subjects who exceed the maximum daily OCS dose at the Week 12 or Week 24 visits may continue to receive IP if the current dose is part of a temporary increase in OCS dose (eg, protocol-allowed burst and taper). Subjects who cannot be returned to their pre-increase dose within 14 days from the start of the increase will have their IP discontinued at the next visit.

3.9.3 Criteria for discontinuation of investigational product during the second year extension period:

Criteria for discontinuing investigational product at Week 52:

Subjects not meeting the criteria to continue in the second year extension will not receive any IP at Week 52 and will complete the study after completing the required follow-up visits.

Subjects meeting the following criteria may continue to receive blinded IP between Weeks 52 and 100.

- (i) Meeting all of the following criteria based on the renal portion of the PRR definition:
 - eGFR is:
 - ≥ 60 mL/min/1.73 m² or no confirmed decrease of eGFR from baseline of $\geq 20\%$
 - Improvement in 24-hour UPCR:
 - For subjects with a baseline UPCR ≤ 3 mg/mg: <1.0 mg/mg
 - For subjects with a baseline UPCR >3 mg/mg: $>50\%$ improvement from baseline and ≤ 3.0 mg/mg

Renal discontinuation criteria must be confirmed in two separate samples. The second measurement should be at least 1 week after the first measurement.

- (ii) No discontinuation of IP
- (iii) Negative HIV test after signing the Main ICF

Criteria for discontinuing investigational product at Week 52, Week 56 or Week 60

- Failure to obtain Pap smear after Week 48 with result available at Week 60 at latest
- Pap smear result not meeting the eligibility criteria (see [Appendix K](#)) at Week 52, 56, or 60 of a Pap smear obtained after Week 48
- Failure to obtain Week 52 QuantiFERON test result by Week 56

Criteria for discontinuing investigational product at Week 60 and later

- OCS >7.5 mg/day (except one OCS burst and taper)
- MMF >2 gm/day or >Week 52 dose, if Week 52 dose <2 gm/day

Subjects who discontinue the IP during the second year extension period will be followed until Week 104 (or for a minimum of 12 weeks after last dose of IP for subjects for whom IP was discontinued within 12 weeks of Week 104).

3.9.4 Criteria for discontinuation of investigational product for reasons other than lack of efficacy at any time during the study

Subjects may be discontinued from IP in the following situations:

1. Subject decision: The subject is at any time free to discontinue treatment, without prejudice to further treatment. The primary reason should be documented as one of the following:
 - (a) Subject is unable to comply with protocol-specified visits and/or procedures due to conflicts not related to clinical study
 - (b) An AE or laboratory abnormality is of concern to the subject, but not clinically significant to physician
 - (c) The subject is concerned about possibility of receiving placebo or ineffective treatment
 - (d) Subject wishes to participate in another clinical study

- (e) Subject is interested in taking a treatment that is not allowed in this study
 - (f) Subject perceives logistics at the clinical site to be unacceptable
 - (g) Other reason
2. Lost to follow-up: must be documented by time and date of telephone calls, e-mails, text messages, numbers called, individuals spoken to if not subject, and at least 2 attempts to contact the subject via certified letter (see Section 3.9.7)
 3. Adverse event that, in the opinion of the Investigator or the Sponsor/Designee Medical Monitor, contraindicates further dosing with IP
 4. Severe non-compliance with the study protocol
 5. The Investigator or Sponsor/Designee Medical Monitor deems withdrawal as being in the subject's best interest
 6. Pregnancy, positive pregnancy test, or subject expresses an interest in becoming pregnant
 7. Isolated HBcAb positivity with HBV DNA above the LLOQ confirmed by the central laboratory
 8. Positive HIV test
 9. Receipt of any medications identified in Section 7.7.2.1
 10. The use of restricted medications listed in Section 7.7.2.2 if the Sponsor/Designee Medical Monitor, in consultation with the Sponsor, determines the subject must be discontinued
 11. A diagnosis of active TB, premature discontinuation of treatment for latent TB, or non-compliance with latent TB therapy. Note: Duration of treatment for latent TB should follow the local practice. If local practice is not defined, then Centers for Disease Control and Prevention (CDC) guidance for immunocompromised patients should be used.
 12. Subject is unblinded by the Investigator

Additional restrictions related to concomitant medications are discussed in Section 7.7.

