Investigators will not be required, but may continue, to taper OCS dose beyond the target of 7.5 mg/day up to Week 40. Steroid tapering will not be permitted from Week 40 to Week 52.

Steroid “burst and taper”

A steroid burst is defined as one of the following:

Oral corticosteroid increase up to a maximum daily dose of 0.5 mg/kg/day (maximum 40 mg/day) prednisone-equivalent dose for up to a total of 14 days and that must be fully administered and tapered to less than or equal to the pre-burst starting dose by the end of the 14th day. Any course of OCS burst must not extend beyond Week 40 during the first year (starting after Week 0) and Week 92 during the second year extension period (starting after Week 52), regardless of when the course was started.

OR

A maximum of 1 instance of intra-articular, tendon sheath or bursal injections (for a total methylprednisolone \leq 80 mg or equivalent) can be given. Subjects who receive any intra-articular/tendon sheath/bursal injections should not receive OCS burst (and vice versa).

Steroid burst is allowed as follows:

- **From randomisation to Week 40:** One burst and taper of corticosteroids for increased SLE disease activity or for non-SLE activity is allowed.

Subjects who receive more than one steroid “burst and taper” or who violate the above criterion may continue to receive IP after approval by Sponsor/Designee Medical Monitor, but will be considered non-responders for subsequent responder analyses (such as CRR), regardless of whether the OCS “burst” was administered for increased SLE activity or non-SLE causes.

- **Increase in corticosteroids from Week 40 to Week 52:** No increase in OCS, or the use of IV or intra-articular, tendon sheath or bursal injections is allowed from Week 40 until Week 52 assessment.

Corticosteroid dose from Week 52 to Week 100

- If the OCS dose is >7.5 mg/day at Week 52, tapering to ≤ 7.5 mg/day is required by Week 60. Failure to achieve ≤ 7.5 mg/day by Week 60 will lead to discontinuation from IP.
- OCS dose must be tapered to ≤ 5 mg/day at Week 80. OCS tapering below 5 mg/day is allowed at any time until Week 92.
- No change in OCS dose will be allowed from Week 92 to Week 104.
- One burst and taper will be allowed between Week 52 and Week 92.

Increase in corticosteroids for the prevention of adrenal insufficiency

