For a severe illness, surgery, or symptoms of adrenal insufficiency, if clinically warranted, the following can be used, in addition to the “burst and taper” described above:

- Oral or IV hydrocortisone up to 100 mg every 8 hours on the first day followed by half that dose for 2 days before returning to their usual dose or
- Subjects who are taking ≤ 7.5 mg/day prednisone or equivalent will be allowed to receive up to an additional 7.5 mg/day to a total of 15 mg/day oral prednisone or equivalent for a total of up to 14 days.

Subjects who receive either of these corticosteroid regimens for the prevention of adrenal insufficiency between Week 40 and Week 52 will be considered as a non-responder for the Week 52 analyses.

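### From Week 60 the OCS stop rule makes no exception for the adrenal-insufficiency cover that 7.7.3.2 permits on top of the burst, so a subject whose Year 2 burst is used can lose IP for a permitted treatment

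*Protocol*

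**What the plan says.** **Stop rule.** Protocol 3.9.3 lists, among the criteria that apply from Week 60 onwards, "OCS >7.5 mg/day (except one OCS burst and taper". The synopsis and SAP 1.2.5 carry the same criterion with the same single exception.

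**The burst.** Protocol 7.7.3.2 defines an oral burst as an increase "up to a maximum daily dose of 0.5 mg/kg/day (maximum 40 mg/day) prednisone-equivalent dose for up to a total of 14 days", tapered back within that time. A course "must not extend beyond Week 40 during the first year (starting after Week 0) and Week 92 during the second year extension period". For Year 2: "One burst and taper will be allowed between Week 52 and Week 92".

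**Adrenal cover.** The same section then says: "For a severe illness, surgery, or symptoms of adrenal insufficiency, if clinically warranted, the following can be used, in addition to the" burst and taper. Two regimens follow. One is "Oral or IV hydrocortisone up to 100 mg every 8 hours on the first day", then half that dose for two days. The other is prednisone: subjects already on 7.5 mg/day or less "will be allowed to receive up to an additional 7.5 mg/day to a total of 15 mg/day oral prednisone or equivalent", for up to 14 days. No study week limits the permission. The only consequence stated is non-responder status at Week 52 when cover is given between Weeks 40 and 52.

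**Late freeze.** The Year 2 steroid list in 7.7.3.2, repeated in SAP 1.2.4, allows no OCS dose change between Weeks 92 and 104. It does not mention adrenal cover.

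**The concern.** The protocol permits a treatment in one section, and another section makes that treatment a reason to stop IP. Adrenal cover is described as additional to the burst, but the stop rule excepts only the burst. Once the Year 2 burst has been used, nothing in 3.9.3 protects a subject who is given the permitted prednisone for surgery or a severe illness.

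Two analysis consequences follow from stopping IP. SAP 4.1.4.3 imputes non-response from premature IP discontinuation, so the subject fails the Week 104 responder endpoints. SAP 4.2.1 dates discontinuation at the last infusion and drops later values from the while-on-treatment analysis of 24-hour UPCR. Neither consequence would reflect the course of the nephritis. Sites could also reasonably act differently, one stopping IP and another continuing it.

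**Working it through.** The plan states no figure on this point, so the check compares sections and adds simple arithmetic.

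**1. Does adrenal prednisone cross 7.5 mg/day?** Inputs: supplement up to 7.5 mg/day, total up to 15 mg/day (7.7.3.2); OCS at most 7.5 mg/day by Week 60 and at most 5 mg/day at Week 80 (7.7.3.2).

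- Background 7.5: 7.5 + 7.5 = 15 mg/day, and 15 / 7.5 = 2.0 times the threshold. Any increase crosses it.
- Background 5: 5 + 7.5 = 12.5 mg/day. Headroom is 7.5 - 5 = 2.5 mg/day, so only a larger increase crosses.
- Background 0: 0 + 7.5 = 7.5 mg/day, which is not above the threshold.

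IV hydrocortisone is not an oral corticosteroid and falls outside the rule. Oral hydrocortisone is not computed here.

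**2. Can the course be recorded as the burst?** The minimum weight at entry is 40 kg (Protocol 3.1, criterion 5). The burst ceiling at that weight is 0.5 x 40 = 20 mg/day for up to 14 days. A 15 mg/day course of up to 14 days fits. So a first course that ends by Week 92 can be accommodated by treating it as the burst, at the price of using the burst up. The clear gap is therefore the subject whose Year 2 OCS burst has already been given.

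**3. What would stopping cost?** Year 2 doses fall at Weeks 52, 56, ..., 100: (100 - 52) / 4 + 1 = 13. Year 2 24-hour UPCR visits are at Weeks 64, 76, 88 and 104 (Protocol 5.1): 4. UPCR is sampled before that day's dose, so a sample on the day of the last dose is kept. Two illustrations with the burst already used:

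| Last dose | Doses lost | UPCR visits lost |
|---|---|---|
| Week 60 | 64 to 100: 10 of 13 | 64, 76, 88, 104: 4 of 4 |
| Week 76 | 80 to 100: 6 of 13 | 88, 104: 2 of 4 |

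The lost UPCR values are still to be collected, and they enter the treatment-policy sensitivity analysis in SAP 4.2.1.

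**4. After Week 92.** No burst may run past Week 92, so the stop-rule exception is unavailable even to a subject who never used it. The freeze on OCS dose also applies. The text therefore gives two answers on whether cover may be given at all. At most the Week 96 and Week 100 doses and the Week 104 UPCR visit are at stake for a subject whose last dose is Week 92 (2 of 13 and 1 of 4).

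**5. Reach.** The rule starts at Week 60. SAP 4.2.1 fits the Week 52 UPCR model to data up to Week 52 only, and CRR at Week 52 is fixed before the rule applies. The primary and secondary analyses and the testing hierarchy are untouched.

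**The case against.** **The specific permission may qualify the general rule.** A sensible site could read 7.7.3.2 as overriding 3.9.3. Protocol 8.5 gives some support: it assigns non-response to additional Year 2 bursts, which would be largely redundant if each one ended IP. This bears on intent and stands as a reason not to call IP loss automatic. It does not reconcile the text, because 3.9.3 names one exception and 8.5 speaks of remaining in the study, not on IP. The discretion in 7.7.2.2 covers steroid increases beyond what the protocol allows, and the approval route for extra bursts in 7.7.3.2 is written for randomisation to Week 40. Neither addresses permitted cover in Year 2.

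**The trigger may be visit-based.** Visits are four weeks apart and a 14-day course could fall between them. The Week 12 and 24 rule in 3.9.2 is tied to visits; the Week 60 rule does not say. This stands: the losses above assume that the rule is applied whenever the dose exceeds the threshold.

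**The Year 1 comparison is limited.** The Week 12 and 24 rule exempts any temporary increase, with the burst as an example. Its thresholds are about 15 mg/day, the cap on adrenal prednisone, so it scarcely meets this case. It supplies usable wording but does not prove an oversight.

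**Some responder loss may occur anyway.** A course above 7.5 mg/day after Week 80 already fails the sustained-reduction limit of 5 mg/day. After Week 92, cover might itself count as non-response, by analogy with Weeks 40-52. SAP Appendix B, which holds the corticosteroid criteria, is not in the text available.

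**Stronger readings a reader might infer.**
- That a joint, tendon-sheath or bursal injection uses up the exception. Section 7.7.3.2 says subjects given such "injections should not receive OCS burst (and vice versa", but the stop rule refers to an OCS burst, so this is only one reading.
- That a course after Week 92 is plainly permitted and plainly ends IP. The freeze makes the permission itself unsettled.
- That recording cover as the burst makes a later lupus burst certain non-response. Protocol 8.5 says so; SAP 4.1.4 says only that such subjects may be so considered.

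**Conclusion.** The inconsistency is real and is repeated in all three statements of the rule. Taken literally, a subject in Year 2 who has used the OCS burst, and whose permitted adrenal prednisone takes the total above 7.5 mg/day, meets an IP stop rule. Week 104 non-response and loss of later on-treatment UPCR values then follow. For Weeks 92-104 the documents support only the narrower statement that the permission and the freeze conflict.

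Severity is minor. The trigger needs an intercurrent illness or surgery, oral treatment above the threshold and a burst already used. The documents give no rate for this, so no share of subjects is estimated, and the 10-of-13 case is an illustration near the worst end. Only Year 2 management and exploratory Week 104 outcomes are affected. Confidence is high in the textual mismatch and lower in how often, or whether, sites would act on it. The conclusion rests on a literal reading of 3.9.3, a trigger not confined to visits, and nothing in the unseen Appendix B that settles the matter.

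**What to change.** 1. In Protocol 3.9.3, the synopsis and SAP 1.2.5, keep the existing exception and add: *or an adrenal-insufficiency regimen allowed in 7.7.3.2 that returns to the prior dose within 14 days*.
2. In the Week 92-104 OCS sentences (Protocol 7.7.3.2 and SAP 1.2.4), add: *except an adrenal-insufficiency regimen*.
3. State the Week 104 responder status of subjects given such cover in Weeks 92-104, as 7.7.3.2 already does for Weeks 40-52, and check that SAP Appendix B agrees.

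The first change alone would leave the late freeze in conflict, so the second is needed with it. The cost is one clause in three places, one clause in two more, and a sentence on responder status. No new data, visits or subjects are required.
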